e-Natureza: Affective Validation of Nature Images as a Complementary Resource for Promoting Well-being in Hospital Environment

PROTOCOL

Sao Paulo, Brazil

Approved in the first version in 01/31/2017

Human subjects protection review board number: Hospital Israelita Albert Einstein Research Ethics Committee 64096816.9.0000.0071.

1. Summary

Of all the animals that inhabit the earth, man is the only one that has a differentiated relationship with nature. Besides belonging to it, like other species, it has established, throughout its trajectory, other relations in search of understanding it, dominating it, exploiting it, whether for the purpose of survival, recreation, financial enrichment or even conservation

The establishment of power relations in relation to the surrounding nature without the necessary awareness of the inevitable consequences has led to the critical thresholds that have been widely discussed, today, on the aegis of environmental sustainability. Sustainability is understood here as the maintenance of the functions and components of the ecosystem, in a sustainable manner and can also be referred to as the ability of the natural environment to maintain living conditions for people and other species and the quality of life for humans, taking into account habitability, the beauty of the environment has as main objective to stimulate the best in individuals and in the environment for the present and an unknown future. Although an evolving concept, it seeks to ensure that future generations have access to natural resources (Our Common Future, 1998), many of which are currently under threat.

This is a relevant aspect and the most addressed in the literature, but there is another one of fundamental importance that is characterized by the interrelationship between nature and human health conditions.

From the very beginnings of existence the idea that contact with nature provides harmony and balance to human beings is quite common. It is also clear that this relationship can also cause suffering, for example in situations involving animal accidents or natural disasters.

It is a fact that, over time, man by adopting new lifestyles (not always so healthy) has been moving away from the contemplative moments with nature and, consequently, of its possible benefits on physical, mental, emotional and spiritual. The contemporary lifestyle has generated stressful living conditions, which is reflected in physical and psychic illness, which includes cardiovascular disease, obesity or burnout. Such an impact on health has led to the need to understand and prevent the deleterious effects associated with modern life in societies (Joye, Pals, et al, 2013).

On the other hand, especially in large metropolises, there is little room for discussion on this theme, since this distance tends to suppress the need for a more accurate look at the human-nature dyad in the perspective of health.

A review of the literature that included 57 studies revealed that this topic has been little investigated by the health sciences, with social and environmental sciences being the subjects responsible for the greatest scientific production in this area. It is also worth noting that North America and Europe have the highest number of surveys (79%), and no studies are found from South America or Africa (Keniger, Gaston, et al. 2013.), Although both have a rich biodiversity.

The hypothesis that humans have an inherent inclination to contact with nature has been termed biophilia. The relationship between man and nature is represented in some way in all cultures. In the first European hospitals, gardens were considered an essential part of the environment to aid in the therapeutic processes (Grinde, Patil; 2009).

Interactions with nature can occur in three ways: a) Indirect interaction, which does not require the person to be physically present in nature and may include activities such as observing nature in a photograph or picture or seeing nature through a window; 2) incidental interaction, in which the individual is physically present, but comes in contact with some element of nature in an unintentional way, it is the result of another activity (example: contacting a plant pot in a working environment); and 3) intentional interaction in which the individual is environment); and 3) intentional interaction in which the individual individual intentionally seeks contact with nature, such as observing wildlife, gardening, or visiting a park (Keniger, Gaston, et al; 2013).

Many people seek nature when they feel stressed. Nature-based coping strategies appear to be effective and there are an increasing number of studies demonstrating that contact with nature may have health benefits (Berg, Mass, et al., 2010). These benefits include positive effects on mental processes

(increase of self-esteem, improvement of mood, reduction of negative moods, reduction of anxiety and promotion of psychological well-being); positive effects on cognitive abilities (reduction of mental fatigue, restoration of attention) and positive effects on physical function and health (reduction of stress, blood pressure, cortisol levels, headaches, among others) (Keniger, Gaston, et al. al; 2013). The contact with natural elements, according to some theorists, produces a type of fascination that is characterized by a moderate intensity and, generally, centered in aesthetically pleasing stimuli that allow the opportunity of reflection promoting in a more efficient way the restoration of the attention (Gressler, Gunther, 2013).

These studies have sought to identify the influence of natural environments on health, but it is not always possible to be in touch with nature to enjoy its potential benefits. Particular situation is constituted by the processes of illness, in which the individual, even if he wanted, is unable (sometimes for long periods) to interact with natural environments.

In nursing, since Florence Nightingale, there is a strong concern to make hospital environments in restorative environments. Florence already stressed the importance of the patient getting up or turning in bed and see through a window, the sky and the sunlight, at least if it cannot be shown anything else, claiming to be such a measure of prime importance for the recovery, or something very close to it (Nightingale, 1898).

Have, in the hospitalization unit, a window overlooking a natural landscape has been shown to be an adjuvant potential in the recovery of surgical patients, by reducing the consumption of analgesics and a shorter hospital stay (Ulrich, 1984).

But the hospital buildings, in the urban context, do not always provide a "window with a view." When we think of health institutions, especially those that do not have green areas, which patients could benefit from, it has directed researchers to other forms of contact that may bring some degree of well-being to patients during the hospitalization, among them the use of photographs and videos (accompanied or not by music), in the perspective of an indirect interaction.

Therefore, audiovisual resources are beginning to be investigated, as well as commercial devices that create "virtual windows" are also being developed. However, access to these resources is very restricted in our environment, either due to lack of knowledge or due to economic and financial constraints.

The randomized clinical trials conducted with patients using natural-based audiovisual interventions are also incipient. Eighty patients submitted to bronchoscopy were exposed to static scenes and sounds of nature before, during and after the procedure and presented significant reduction of pain during the procedure. The mural was purchased commercially from a specialist company and consisted of a quality (42; 52-inch) photograph of a mountain and a stream crossing the field lying next to the patient's bed during the procedure, accompanied by sounds of birds and of water, ears with earphones (Diette, Lechtzin, et al; 2003). Thirty-seven patients were also submitted to audiovisual stimulation and presented reduction of abdominal discomfort during sigmoidoscopy (Lembo, Fitzgerald, et al., 1998). Reduction of pain and anxiety was also observed during dressing in a small sample of patients with burns when submitted to video programs with nature scenes and music (Miller, Hickman, Lemasters, 1992). However, in addition to the small sample participants, methodological failures related to randomization and blinding were found, as well as criteria for selection of poorly established images (Drahota, Ward, et al., 2012).

If on the one hand the potential of the images of nature in the production of well-being has already been discussed and demonstrating its therapeutic potential and on the production of emotions, on the other hand, there is a difficulty, in clinical practice, in selecting which images can assist in diverse clinical situations, because there is no bank of images that are validated and intended for this purpose.

The studies have not clearly indicated the selection criteria of the images used. They are usually thematic and landscape images, such as beaches, mountains, forests, which represent natural environments of the countries in which they are developed. This leads us to some reflections on the constituent elements of these images. Would the contribution of each natural element be similar in the same landscape? Observe, for example, photographs of birds, would be different to observe flowers? Which of these, among other visual reasons of nature, would have greater potential to trigger benefits? What kind of emotions do they trigger in the observer? It is necessary, therefore, to have some indicator to mark the selection of images for studies that aim their application in clinical practice.

In this sense, another motivating aspect for the development of this study is the fact that the largest bank of images with validated emotions can not be published or divulged, much less make it available for clinical use, since its access is restricted to researchers. The International Affective Picture System (IAPS) is a library of images with hundreds of color photographs that represent various aspects of real life (sports, fashion, landscapes, violence, etc.) with the aim of evoking emotional states that can be easily presented in the experimental context of the laboratory, thus allowing accurate control over the timing and duration of exposure (Bradley, Lang, 1999; Lang, Bradley and Cuthbert, 2005). In Brazil, IAPS normative scores were evaluated with 707 images of Brazilian university students, with the purpose of using them in the investigation of cognitive processes in normal individuals and in populations with neurological and affective dysfunctions (Ribeiro, Pompéia, Bueno, 2004).

Another four sets of images are described in the literature: Geneva Affective Picture Database (GAPED), EmoPics, Nencki Affective Picture System (NAPS) and Open Affective Images (OPAFI).

It is common to all these bases: formal access required, exclusive to researchers, for use restricted to scientific studies, without commercial use. The images can not be published and all the banks are asymmetrical, formed more by negative than positive images. These banks, therefore, are unique to research and can not be used in clinical practice, the main reason for the realization of the present study. In the hospital context, our interest also falls on images that have the potential to promote states of well-being and comfort.

Besides knowing, the emotional responses, another relevant aspect to be questioned is if individuals more related to nature evaluate more positively the images of nature. On the other hand, exposure to images of nature can increase the feeling of connection with nature? Knowing this relationship is of particular importance not only for the use of images of nature as a potential resource of balance for human health, but also for uncovering ways to improve the man-nature relationship, in order to preserve it as well, thus expanding the relevance of the production and dissemination of validated images.

There are clinical situations for which we believe that interventions based on nature may be particularly useful, among them, when patients undergo chemotherapy.

Chemotherapy can cause a crisis in the patient's life, with physical and psychic impacts. In clinical use it is generally well tolerated by patients and moderate side effects are well controlled with appropriate dosages and judicious use of other drugs such as antiemetic's (Sawada, 2009).

On the other hand, emotional aspects can be ignored and more difficult to control. Some emotional reactions such as anxiety, depression and emotional distress can be observed during chemotherapy (Baker-Glenn, et al., 2010). Infusion time can be very distressing, but it can also be seen and experienced as a period of seclusion and rest. For many patients it is distressing because it can mean imprisonment or incapacitation to perform the tasks. He also appeals to discourse of boredom, lack of what to do (Sette, Gradvohl, 2014). Some researchers concluded that levels of emotional distress during chemotherapy are high, suggesting a clinical need for interventions to provide support to patients during chemotherapy (Decat et al., 2010).

Helping patients find effective strategies for dealing with chemotherapy is an important task for nurses. Complementary interventions to pharmacological treatment aim to reduce suffering at different stages of treatment.

Based on these scenario, we seek therefore produce and study an image database and validate them scientifically, aiming initially the care settings, in order to produce well-being for patients undergoing chemotherapy, as well as deepen our knowledge of man-nature connection, from the perspective of care, self-care and preservation.

2. Objectives

Verify the therapeutic potential of the validated images in the reduction of negative mood states and increase of positive states of patients undergoing the chemotherapy session.

Verify the therapeutic potential of the validated images in the treatmentrelated symptoms during the chemotherapy session.

Verify if the rate of connection with nature influences the impact in the study outcomes.

3. Design and methods

The previously validated e-Natureza image bank consists of licensed images by nature photographers who volunteered to contribute to the development of the project. They are photos with predominance of flowers, colorful birds, white birds, landscapes, photos with predominance of trees, predominating the element water, with predominance of sky, photos related to the sea, totaling 480 images.

The final image bank consists of the validated images that reached the low alert and high valence scores, that is, photos that were concentrated in the lower right quadrant of the figure below, with a view to promoting well-being and tranquility.

[figure not shown]

Figure 1 - Distribution of 360 images of International Affective Picture System (IAPS).

The randomized clinical trial will be conducted at the same institution, Albert Einstein Hospital, that the nature images were validated. The date collection of the clinical trial will be done in a period of 12 months, together with a convenience sample of patients, of both sexes, who is over 18 (eighteen), with clinical conditions and communication systems preserved, in other words, lucid, that allows the participation in the study and who are undergoing the first session of the chemotherapy treatment (most patients in the first session, have an altered emotional state, be it for fear, anxiety) independently of the type of oncological disease.

The patients, after understood and signed the Informed Consent Form will respond to a questionnaire with sociodemographic and clinics variables (gender, age, marital status, schooling, profession, relationship with nature, diagnosis, treatment time, protocol type) for characterization of the sample (Appendix I).

The patients will be allocated randomly into two groups: 1) control and 2) intervention group through Randomizer® software.

After thirty minutes of the start of the chemotherapy session, the patient you will receive a notebook (specific to the study and blocked for other functions) that he can watch a presentation of nature images. It will be four videos with fifteen minutes each one.

At the beginning and at the end of the chemotherapy session, each patient will make an assessment of the positive and negative affects and the physical and psychological symptoms related to that chemotherapy session.

According to Paschoal and Tamayo (2008), measures of affection reflect how much the person feels enthusiastic, alert and active. The negative affect reflects how much the person feels displeasure and distress. According to these authors, one of the main affective measures used in study of general well-being is the Positive Affect/Negative Affect Scale, which through 20 words that describe feelings that should be answered on a five-point scale: "very little or nothing", "a little", " moderately", " too much", and "excessively", allowing use as a measure of state or trace. In Brazil, PANAS (Annex I) was adapted for the adult population by Giacomoni and Hutz and for adolescents by Segabinaz et al (2013), already validated elderly people in a virtual environment.

The evaluation of symptoms during the chemotherapy session also will be evaluated by - Edmonton Symptom Assessment Scale – ESASBr - (Annex II).

The Edmonton Symptom Assessment System (ESAS) is a widely used multi-symptom assessment tool, developed for the first time in 1991 by Bruera et al. to audit the symptoms of patients receiving palliative care. The ESAS is a viable, valid and reliable multi-symptom assessment tool for use in Brazil (Paiva, et al, 2015).

The participants will also respond pre intervention to the Nature Connection Scale and Nature Relatedness Scale (Annex III and IV) because it is a variable that can interfere in the study's outcomes of interest.

The control group will undergo the same evaluations as the intervention group and at the same time interval during the chemotherapy session.

All evaluations will be performed in only one chemotherapy session.

4. Statistical analysis plan

Descriptive statistics will be applied to sociodemographic and clinical data of the study, with calculation of means and standard deviation.

By means of inferential statistics, a comparison will be made between the states subsequently presented by the patients in the clinical trial, using SPSS statistical software. For analysis correlation will be used the Spearman and Pearson tests; for averages comparison if the sample is normal, the paired t-test will be used; for nonparametric sample the Wilcoxon test, and the Fisher and chi-square tests for compare proportions. The tests will be considered significant when p <0.05.

5. History of changes

- Research Project- Version 1- submitted to Research Ethics Committee of the Hospital Israelita Albert Einstein in December 23, 2016;
- Informed Consent Form Patient- Version 1- submitted to Research Ethics Committee of the Hospital Israelita Albert Einstein in December 23, 2016;
- Documentation approved by the Research Ethics Committee of the Hospital Israelita Albert Einstein in the first version at a meeting held in 01/31/2017.
- Documentation disapproved by ClinicalTrials.gov in the first version in 03/16/2017;
- Documentation disapproved by ClinicalTrials.gov in the second version in 03/28/2018;
- Documentation disapproved by ClinicalTrials.gov in the third version in 04/16/2018.

6. Research ethics committee original report translated to English*

*The original one is in Portuguese

HOSPITAL ISRAELITA ALBERT EINSTEIN- SP

CONSUBSTANTIATED TECHNICAL ADVICE OF RESEARCH ETHICS COMMITTEE

RESEARCH PROJECT DATA

Research title: e-Natureza: Affective Validation of Nature Images as a Complementary Resource for Promoting Well-being in Hospital Environment

Researcher: [name]

Thematic area:

Version: 1

CAAE: 64096816.9.0000.0071.

Proponent institution: Hospital Israelita Albert Einstein-SP

Principal Sponsor: Hospital Israelita Albert Einstein-SP

TECHNICAL ADVICE DATA

Technical advice number: 1.906.315

Project apresentation: In recent decades there has been a growing interest of researchers in understanding how the adoption of natural elements of daily life, including in hospital institutions, can characterize restorative environments and reflect in better health conditions for patients. Contact with nature can be done through photographs. However, there is no database of validated nature for clinical use (only for restricted use in research). This study aims to validate images of nature and verify its therapeutic potential in the care of cancer patients undergoing chemotherapy. Therefore, the research is divided into two phases. First we will build a web tool that allows the validation of nature photographs in accordance with international validation method. This phase will be conducted with students and health professionals as well as individuals from

the general population. The validated photographs will compose a database of images of which low activity and positive valence images will be used in the randomized clinical trial with patients on chemotherapy treatment. Anchored with assumptions from the theory of biophilia, from Florence Nightingale's environmental theory, our hypothesis of study is that this intervention promotes subjective well-being and favors more positive moods, in addition to reducing symptoms.

Research Objectives:

Contribute to the validation of images of nature for clinical use in health institutions

Specific:

1-Develop a tool that allows the application, in a web environment, of the affective classification of images of nature, according to the Self-Assessment Manikin method (SAM).

2-Validate the images of nature with students and health professionals and individuals of the general population.

3-Compare the scores obtained with similar photos that compose the IAPS image bank.

4-Verify if the factor related to nature and kinship with nature influence the affective validation of images.

5-Create an audiovisual nature image resource (e-nature) for clinical use in patients undergoing chemotherapy treatment.

6-Verify the therapeutic potential of the validated images in the reduction of negative mood states and increase of positive states of patients undergoing chemotherapy.

7-Verify the therapeutic potential of validated images in the reduction of treatment-related symptoms during the chemotherapy session.

8-Know the patient's perception about the intervention based on nature.

Assessment of risks and benefits:

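### Does PANAS overlook the calming effect for which the nature images were selected?

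*Combined protocol and SAP*

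**What the plan says.** Section 3 (Design and methods) sets the rule for choosing pictures: "The final image bank consists of the validated images that reached the low alert and high valence scores", and gives the purpose: "with a view to promoting well-being and tranquility".

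The first objective in Section 2 has two halves: "reduction of negative mood states and increase of positive states of patients undergoing the chemotherapy session". The hypothesis, given in the ethics committee report reproduced in Section 6, is broader: "our hypothesis of study is that this intervention promotes subjective well-being and favors more positive moods, in addition to reducing symptoms".

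Section 3 gives the reason for the instrument: "one of the main affective measures used in study of general well-being is the Positive Affect/Negative Affect Scale". It also says that "measures of affection reflect how much the person feels enthusiastic, alert and active". The next sentence of the protocol turns to negative affect, so this one is fairly read as describing the positive side, although it does not say so.

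On timing, Section 3 says: "At the beginning and at the end of the chemotherapy session, each patient will make an assessment of the positive and negative affects". Symptoms are rated at the same two points, and the control group has the same assessments at the same interval. On the patients, Section 3 notes that most of those at a first session "have an altered emotional state, be it for fear, anxiety".

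**The concern.** The pictures were filtered for low arousal, and the positive half of the first objective is measured by a score described as enthusiasm, alertness and activity. One positive row in Annex I, Alert, even shares its name with the dimension on which the pictures were chosen to be low. If viewing made patients feel pleasant and calm without making them more activated, the positive score could stay flat or dip. A reader might then report no gain in positive states for patients who did feel better. At stake would be the reading of one of the trial's outcome scores.

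**Working it through.** The plan gives no figure to reproduce here: it states no sample size, standard deviation or effect size. The check is a count of rows, followed by a comparison of what was selected, what was asked and what is measured.

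**1. Count of the PANAS rows in Annex I.**
- Positive (9): Alert, Attentive, Determined, Excited, Excited, Inspired, Interested, Strong, Proudly.
- Negative (9): Afraid, Ashamed, Afflicted, Guilty, Hostile, Uneasy, Nervous, Terrified, Upset.
- Visible rows: 9 + 9 = 18. Section 3 states 20 words, so 20 − 18 = 2 are not visible.
- Visible positive rows that name calm: 0 of 9.

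**2. How firm that count is.** If both unseen words were positive and calm, calm would be 2 of 9 + 2 = 11 positive rows. Excited is printed twice. If one of the two is a mistranslated word of unknown content, the upper bound becomes 3 of 11. The lower bound is 0. The observation is therefore correct for the list as printed, and that list is an incomplete translation.

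**3. What the trial sets out to show.** Tranquility appears in Section 3 as the purpose of the picture filter. Neither the objectives in Section 2 nor the hypothesis in Section 6 makes calm an outcome. They name less negative mood, more positive states, subjective well-being and fewer symptoms. PANAS gives a positive and a negative score, which match the two halves of the first objective.

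**4. Where calming would show.**
- PANAS negative rows that calming could lower: Afraid, Afflicted, Uneasy, Nervous, Terrified, Upset, which is 6 of the 9 visible.
- ESAS rows in Annex II: anxiety and well-being, 2 rows.
- Both scales ask about the present moment and are completed at the start and end of the session in both arms.

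Section 3 expects most patients to arrive frightened or anxious. For them, becoming calm means a fall on exactly these rows.

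**5. Direction.** The low-arousal score was given to pictures by validation raters. It is not a patient's state after an hour of viewing (four videos of fifteen minutes). Section 1 lists less mental fatigue and restored attention among the benefits of nature, and describes boredom during infusion. Both are reasons why rows such as Attentive or Interested could rise. The documents do not settle which way the positive score would move.

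**6. Size.** An illustration is possible only with inputs that the documents lack. Assume item SD 1, inter-item correlation ρ of 0.3 to 0.5, and a shift of 0.5 SD on m of k = 9 positive rows. The standardised effect on the sum is d = 0.5m / √(k + k(k − 1)ρ).
- m = 9: 4.5/√30.6 = 0.81 to 4.5/√45 = 0.67.
- m = 3: 1.5/√30.6 = 0.27 to 1.5/√45 = 0.22.
- m = 0: d = 0.

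This shows only that the score responds less when fewer of its rows respond. How many rows the pictures move is unknown, so no loss can be claimed.

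**7. Any decision rule.** Section 4 names the tests and a 0.05 threshold. It names no primary outcome and contains no rule by which a flat positive score decides that the images do not calm.

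**The case for a change.** The strongest case for the concern is this. Falls in fear or anxiety answer the negative half of the first objective, and ESAS serves the symptom objective. Neither is assigned to the positive half, which is left to a score with no visible calm row. Section 4 does not say that the scores are to be read together, so a flat positive score could be reported as no gain in positive states. A single prespecified sentence, or two extra self-ratings of pleasantness and arousal, would guard against that at little cost.

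The count behind this stands, and so does the caution that a flat positive score must not be reported as absence of calming. But no gain in positive affect as PANAS measures it would be a correct statement of that result. The other scores would be in the same dataset for any reader to set beside it.

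An interpretive sentence would change no data, test or estimate. It also carries a risk: with no order of importance among the scores, any one of them could be used to rescue a flat result.

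Extra ratings are a matter of preference. They add 2 items to the 18 + 9 = 27 rows shown (2/27 = 7.4%), or to the 20 + 10 = 30 items stated (2/30 = 6.7%), at each of two times. The documents use the Self-Assessment Manikin only to rate pictures, so its use as a patient state rating would be new here. Low arousal as a target could be hard to tell from the drowsiness and tiredness that ESAS scores as symptoms. It also presumes a direction that step 5 leaves open.

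The ethics report lists an aim of learning how patients perceive the intervention. No method for it is described, so it is weak cover, and the conclusion does not depend on it.

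**Conclusion.** The concern does not hold. The plan measures the mood states and symptoms that its objectives and hypothesis name, with an instrument it justifies, at both times and in both arms. The absence of a calm row among the 9 visible positive rows is real (0 of 9, at most 2 of 11 if both unseen words were calm, and at most 3 of 11 if one Excited is also a mistranslation). It limits what the positive score can say, but does not make that score wrong. No bias, loss of power or wrong test follows, and no size or direction can be derived from the documents.

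This rests on three assumptions: that the positive and negative PANAS scores and ESAS are all reported as collected, that Annex I is read as printed, and that the sentence on enthusiasm and alertness describes positive affect. The conclusion would differ if the protocol had made calm a trial outcome, or had let the positive score alone decide whether the images work. It does neither. Other questions about Section 4, such as the lack of a primary outcome or the choice of tests, are separate and are not judged here.

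### Would a null end-of-session result be unreadable because no session times or video viewing are recorded?

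*Combined protocol and SAP*

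**What the plan says.** The Objectives (Section 2) concern mood and treatment-related "symptoms during the chemotherapy session".

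Section 3 then sets this sequence:

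- **Outcome timing.** "At the beginning and at the end of the chemotherapy session, each patient will make an assessment of the positive and negative affects"; symptoms are rated on the same two occasions. Annex I (PANAS) and Annex II (ESAS) both ask for the patient's present state.
- **Intervention.** The patient receives a notebook "After thirty minutes of the start of the chemotherapy session", described in the words "that he can watch a presentation of nature images". On the amount: "It will be four videos with fifteen minutes each one". The text does not say whether all four are meant to be seen.
- **Controls.** They have the same evaluations "at the same time interval during the chemotherapy session".
- **Single session.** "All evaluations will be performed in only one chemotherapy session".
- **Recorded variables.** The baseline list ends with "diagnosis, treatment time, protocol type". Appendix I shows that the second of these means months of treatment for the cancer, not minutes of infusion.

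Patients with any cancer type may enter, and no session length is stated. Section 4 plans no summary of viewing or timing.

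**The concern.** Both scales measure a momentary state, yet they are completed at a point fixed by the infusion and not by the videos. A patient with a long infusion might finish watching hours before the final forms. A patient with a short one might not have time for all four videos, and any patient might watch little. If the trial finds no difference, a reader will ask whether the images do not work, were hardly seen, or worked and wore off. Those answers lead to different next steps. Protocol type may hint at session length but says nothing about viewing. The ethics report (Section 6) lists patients' perception of the intervention as an objective, but no available instrument measures viewing.

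**Working it through.** The documents give no sample size, power, effect size or session length, so there is no stated figure to reproduce. The timing can be bounded.

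**Inputs from Section 3:** start of viewing = 30 min; video length = 15 min; number of videos = 4. **Assumed:** session length T.

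**Earliest end of viewing k videos** = 30 + 15k. For k = 1 this is minute 45; for k = 4 it is 30 + 60 = minute 90.

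**Videos that fit before the final forms** = min(4, (T − 30)/15), in whole videos:
- T = 60: 30/15 = 2
- T = 75: 45/15 = 3
- T = 90: 60/15 = 4

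**Gap from last video to session end** lies between 0 and T − 30 − 15k:

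| Assumed T (min) | k = 1 | k = 2 | k = 3 | k = 4 |
|---|---|---|---|---|
| 120 | up to 75 | up to 60 | up to 45 | up to 30 |
| 240 | up to 195 | up to 180 | up to 165 | up to 150 |

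So exposure and gap can vary widely, even at a known session length. Three questions decide whether that calls for a change.

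1. **Does it bias the comparison?** No. Both arms are assessed at the start and end of the session. Session length depends on the regimen, which random allocation balances in expectation. Partial viewing and delay are part of the intervention as delivered. The quantity estimated is the effect of offering the videos on state at the end of the session, which fits the Objectives.

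2. **Would logging alter the result?** No. As an illustration on assumed values only (standardised difference 0.5, two-sided 0.05, 63 per arm), power is 80%. If low viewing or fading left 75%, 50% or 25% of the effect, power would be about 56%, 29% or 10%. Those figures are the same whether or not viewing is logged.

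3. **Would logging separate the explanations?** Only in part. Consider five fields: session start and end in both arms, plus hand-over time, videos watched and end of viewing in the intervention arm. The count would reveal low exposure. A gap summarised in one arm, arising after randomisation, cannot distinguish an effect that faded from one that never occurred. None of the five records when PANAS or ESAS was completed, so they would give neither the exact gap to the forms nor proof of the equal interval promised for controls. With no sample size in the available text, imprecision is a further explanation for a null, and these fields do not touch it.

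**The case for a change.** The strongest case for acting is that the records are cheap (five fields and one descriptive table), leave entry, allocation and intervention alone, and concern a single session, so viewing not noted then is hard to recover. A positive result would gain too, since readers could see how much viewing lay behind it.

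Much of this stands. The available text has no such fields, the treatment-time variable does not supply them, and a viewing count would be informative. But the argument is for richer description and identifies no fault in the planned comparison. It also infers a gap from what a baseline questionnaire omits: viewing happens after randomisation and would not be expected in Appendix I. No full data-collection form is shown, and some text between the ethics report and Appendix I was not available. The single-session rule limits evaluations; it does not rule out taking session times from hospital records, though the plan mentions no such source. Finally, incomplete viewing has no fixed meaning while Section 3 leaves open whether all four videos are intended.

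**Conclusion.** No change to the plan follows. The observation is accurate: full viewing cannot end before minute 90, the gap to the final forms is unbounded by the text, and no available field records times or viewing. Its consequence is limited to how a null would be described. The loss of effect cannot be derived and may be zero; every session length and power figure above is an assumption.

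The conclusion rests on both arms being assessed on the same schedule, as Section 3 states, and on patients being compared by allocated group. The plan names no main outcome, and Section 4 does not name a test of means between independent groups. Those are separate questions that a viewing log would not settle.

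A team may sensibly note session times, form completion times and videos watched, and report them descriptively. That is optional good practice. A null should in any case be reported as no demonstrated effect of offering the videos on end-of-session state, with its confidence interval.
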